2.2 Secondary endpoints

To be assessed using data from the intervention arm *only*:

- 1) Diagnostic accuracy of Cytosponge™
- 2) Performance of Cytosponge™ in detecting severity of BE
- 3) Performance of Cytosponge™ in detecting intestinal metaplasia (IM) of the gastric cardia: based on IM detection by endoscopy of Cytosponge™-positive patients without BE
- 4) Performance of Cytosponge™ in detecting BE or IM of the gastric cardia
- 5) Performance of Cytosponge™ in detecting oesophageal adenocarcinoma (EAC) and gastric cancer
- 6) Sampling adequacy
- 7) Endoscopy referral rates for adequate test results and successful Cytosponge™ swallows
- 8) Patient acceptability of Cytosponge™: willingness to have the test and to have a repeat procedure, number of patients who fail to swallow, cancer worry, long-term emotional or physical harm, perceived risk of EAC, test experience.
- 9) Physician/nurse acceptability of Cytosponge™
- 10) Safety of Cytosponge™
- 11) Performance of repeat Cytosponge™ test

To be assessed using data from the usual care or *both* study arms:

- 12) Number of BE diagnoses missed in the current management
- 13) Number of undiagnosed BE in the general population vs in the group who received Cytosponge™
- 14) Prevalence and incidence of benign oesophageal conditions (BOCs)
- 15) Acceptability of endoscopy
- 16) Number of BE diagnoses for patients with a negative Cytosponge™ result
- 17) Quality control of endoscopic and pathology results

Epidemiological and longer-term objectives (for up to 10 years):

- 18) Prevalence and incidence of BE during the study
- 19) Prevalence and incidence of BE with dysplasia during the study
- 20) Prevalence and incidence of EAC during the study
- 21) Prevalence and incidence of IM and related gastric cancers during the study
- 22) Prevalence and incidence of BE up to 10 years after the study
- 23) Prevalence and incidence of BE with dysplasia up to 10 years after the study

- 24) Prevalence and incidence of EAC up to 10 years after the study
- 25) Prevalence and incidence of IM and related gastric cancers up to 10 years after the study
- 26) Research and development: Genetic and biochemical risk factors for disease progression (germline and somatic variants and other biomarkers) including targeted, exome level and whole genome sequencing

Health economics analysis:

- 27) To undertake modelling to predict the reduction in EAC-related mortality from this strategy (short and long term)

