3.2.3 Non-compliance corrected (ITT) population

An adjustment for lack of Cytosponge™ use in the intervention arm (non-compliance) will be made following the method detailed in Cuzick et al., which gives an estimate of the effect of the intervention for those who attend the Cytosponge™ test invitation. This will show the causal impact of the Cytosponge™ on BE detection.

BE detection in compliers in the intervention arm will be compared to BE detection in potential compliers in the usual care, i.e. participants who would have received the test if they had been offered it. In order to do that, the proportions of actual or potential compliers/non-compliers in the two arms is assumed to be the same, and so is the proportion of BE detection in actual or potential non-compliers. The proportion of BE detection in potential compliers in the usual care arm will be estimated as:

$$\frac{\text{no. BEs in usual care} - \text{no. BEs in potential non compliers}}{\text{no. potential compliers}}$$

Data on number of BEs detected in the two study arms will come from the ITT analysis on the primary endpoint.

The relative protection given by the intervention in those who comply is to be estimated as

$$\frac{S_{11}/N_1}{S_0/N_0 - S_{10}/N_1}$$

where $\{S_0, S_{10}, S_{11}\}$ and $\{N_0, N_{10}, N_{11}\}$ are the numbers of BE detected and the numbers of individuals in the usual care arm, in the non-complier population (intervention) and in the complier population (intervention), respectively.

Note: in order to obtain an estimate of the non-compliance corrected effect, data from the CLR group will be treated in the same way as data from the PLR group, i.e. the two datasets will be merged and the effect of clustering in the CLR group will not be considered. However, in order to obtain confidence intervals for the effect, the variance inflation factor for the study as a whole will be applied to the variance of the effect that ignores the clustering. It is noted that this method assumes that the compliance within cluster is independent of the BE prevalence within cluster. New methodology to better adjust for the clustering may be developed.

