missed cases among those with a negative Cytosponge™. The estimated total number of cases in those with a negative Cytosponge™ is:

$$T_2 = (B_{12} - B_{14} - B_{15} - B_{16}) + B_{11} + 0.25T_1 \frac{N_{12} - N_{13} - N_{11}}{N_{12} - N_{13}}$$

Next, we need to consider how many cases would have been found in those having a Cytosponge™ had they been in the usual care arm. We

assume that those accepting a Cytosponge™ may not have the same rate as in those that did not accept. By subtraction, we estimate

$$T_3 = \frac{B_0}{N_0} (N_{10} + N_{12}) - B_{10}$$

cases among people accepting a Cytosponge™ (had they not been offered a Cytosponge™). So, among those using a Cytosponge™, BE was increased by the factor: $\frac{T_1+T_2}{T_3}$.

As in the intervention arm, we do not simply scale up from the research endoscopies in the control arm. Rather we combine the cases observed directly among those with a research endoscopy, by the expected number amongst the others using the intervention arm to scale up. The scale factor needed $R_0 = \frac{N_0 - N_{01}}{N_{10} + N_{12}}$, i.e. the numbers of people who did not get a research endoscopy in the control arm, divided by the total number in the intervention arm. The total number of cases in the intervention arm is made up of three parts: those observed by research endoscopy plus those in people who would have accepted the Cytosponge™, plus those among people who would not have accepted the Cytosponge™ is offered. The total is estimated as:

$$T_4 = B_{01} + (T_1 + T_2)R + \frac{T_1 + T_2}{T_3} B_{10}R$$

Hence the proportion of BE missed by current management is $\frac{T_4 - B_0}{T_4}$.

- 13) Number of undiagnosed BE in the general population vs in the group who received Cytosponge™:

The number of undiagnosed BEs in the patients who received the Cytosponge™ will be estimated by multiplying the proportion of BEs detected following a research endoscopy in the negative test group by the number of negative test patients.

The number of undiagnosed BEs in the usual care arm will be estimated by multiplying the proportion of BEs following a research endoscopy in the usual care arm by the number of patients in the usual care arm.

The two proportions of undiagnosed BEs will then be calculated out of the total number of patients in each of the two groups and will be compared using a chi-squared test.

- 14) Acceptability of endoscopy:

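### Secondary endpoint 13 tests undiagnosed BE in self-selected Cytosponge acceptors against the whole usual-care arm, so any difference is confounded with who accepted

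*SAP*

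**What the plan says.** Section 2.2 names the endpoint "Number of undiagnosed BE in the general population vs in the group who received Cytosponge™". Section 2.3 repeats that title and gives research endoscopy findings in each arm as the data source.

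Section 7.1.2, item 13, sets the method:

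- Tested group: "The number of undiagnosed BEs in the patients who received the Cytosponge™ will be estimated by multiplying the proportion of BEs detected following a research". The sentence goes on to specify endoscopies in test-negative patients, whose total number is the multiplier.
- Usual care: the proportion with BE at "research endoscopy in the usual care arm by the number of patients in the usual care arm".
- Comparison: "The two proportions of undiagnosed BEs will then be calculated out of the total number of patients in each of the two groups", and these "will be compared using a chi-squared test".

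Two other places in the SAP deal with acceptance. Item 12 of section 7.1.2 says the authors "assume that those accepting a Cytosponge™ may not have the same rate as in those that did not accept", and derives T3, the number of cases usual care would have found among acceptors. Section 3.2.3 compares acceptors with potential acceptors in usual care, meaning "participants who would have received the test if they had been offered it", but limits its inputs: "Data on number of BEs detected in the two study arms will come from the ITT analysis on the primary endpoint". Item 13 uses neither correction.

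**The concern.** Randomisation makes the two arms comparable. It does not make acceptors in one arm comparable with everyone in the other, because the usual-care arm mixes would-be acceptors with would-be refusers. If acceptance goes with BE risk, part of the difference in item 13 reflects who came forward. Section 2.5.1 makes this plausible: it links low uptake to identifying patients by prescribing history, including people without recent symptoms.

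A p-value on this contrast invites comparison as if the arms were intact. The label adds a second problem. The comparator consists of patients selected through reflux prescribing records, so results reported under a general-population heading would be carried to people the trial did not study.

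**Working it through.** The SAP states no expected figure for item 13, so there is none to reproduce. What follows shows how far the contrast could move.

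**Inputs from the SAP.** Section 2.5.2: BE prevalence 4%, usual care diagnoses 0.6%, Cytosponge sensitivity 85%, planned uptake 27%, total recruited 13,234. Section 2.5.3: observed uptake 24.0%. Section 2: 1:1 allocation.

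**Group sizes.** 13,234 / 2 = 6617 per arm if exactly balanced. Acceptors: 0.24 × 6617 = 1588, or 0.27 × 6617 = 1787.

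**Assumptions not in the SAP.** Let r be acceptors' BE prevalence relative to the whole arm. Let s be undiagnosed BE in usual-care research-endoscopy attenders relative to the whole usual-care arm. Test-negative research-endoscopy attenders are taken as representative of all test-negatives.

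**Formulas.**

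- Undiagnosed in the whole usual-care arm: 4% − 0.6% = 3.4%. Item 13 would estimate s × 3.4%.
- Undiagnosed in would-be acceptors under usual care: r × 3.4%.
- Undiagnosed in tested acceptors: r × (1 − 0.85) × 3.4% = r × 0.51%.
- Reduction as written: 1 − (r × 0.51)/(s × 3.4). Like for like: 1 − 0.51/3.4 = 85% at every r.

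| r | s | Tested (%) | Usual care as estimated (%) | Reduction as written | Difference as written (points) | Like for like (points) |
|---|---|---|---|---|---|---|
| 1 | 1 | 0.51 | 3.40 | 85.0% | −2.9 | −2.9 |
| 0.75 | 1 | 0.38 | 3.40 | 88.8% | −3.0 | −2.2 |
| 1.5 | 1 | 0.77 | 3.40 | 77.5% | −2.6 | −4.3 |
| 2 | 1 | 1.02 | 3.40 | 70.0% | −2.4 | −5.8 |
| 1.5 | 1.5 | 0.77 | 5.10 | 85.0% | −4.3 | −4.3 |
| 1.5 | 2 | 0.77 | 6.80 | 88.8% | −6.0 | −4.3 |
| 1.5 | 0.75 | 0.77 | 2.55 | 70.0% | −1.8 | −4.3 |

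With s = 1, the bias follows r. When s equals r, it vanishes. With r = 1.5 fixed, moving s from 0.75 to 2 changes its sign. Neither r nor s can be read from the SAP.

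**Stability of an acceptor-specific alternative.** T3 = (B0/N0)(N10 + N12) − B10. With equal arms, 24% uptake and 0.6% detection in every group, B0 = 6617 × 0.006 = 39.7 and B10 = 0.76 × 6617 × 0.006 = 30.2, so T3 is about 9.5 cases. Its Poisson SD is √(39.7 + 30.2) = 8.4 before any allowance for clustering. The chance that T3 falls below zero is about Φ(−9.5/8.4), or 13%.

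**The case against.** **The SAP does not call the difference an effect of the test.** This is correct. A reader might infer a causal claim from an unadjusted test of tested patients against usual care, but item 13 makes none, and section 3.2.3 is where the SAP addresses causal impact. What stands is that the difference is confounded with acceptance.

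**The bias may be absent.** The usual-care proportion comes from people who attended a research endoscopy, and they may resemble acceptors. If so, the two kinds of selection could cancel. This also stands, and it rules out quoting any single bias figure. It does not rescue the comparison: attending an endoscopy is a different choice from accepting a Cytosponge, and item 13 applies the result to the whole arm.

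**The conclusion would not reverse.** In every scenario above the reduction stays between 70% and 89%, so under the SAP's own sensitivity the tested group still has less undiagnosed BE. The absolute difference moves more.

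**An acceptor-specific comparison should replace it.** A reader might infer that (T1 + T2 − T3)/N12 is the right main analysis. It is weak in that role. When undiagnosed cases after testing are subtracted from T1 + T2 − T3, the missed cases cancel. What remains is cases found among acceptors minus T3, which is close to the section 3.2.3 contrast. The usual-care research endoscopies, the direct evidence on undiagnosed BE in that arm, drop out. T2 also depends on a fixed 80% sensitivity.

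**A supplementary SAP will follow.** Section 7.1.2 says it will give further detail on secondary endpoints. It is not at hand, but item 13 already fixes the groups, denominators and test, and signals no remedy.

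**The label is editorial.** Partly so: section 2.3 and the method text identify the comparator as the usual-care arm. The title in three sections still says otherwise.

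**Conclusion.** The concern holds as a problem of comparability. Item 13 formally tests a self-selected 24% to 27% of the intervention arm against the whole usual-care arm, although item 12 allows that acceptors may differ. The difference cannot be separated from who accepted.

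No size or direction of bias can be given. The scenarios rest on assumed values of r and s and on the SAP's design inputs, and they show bias that is nil, upward or downward. The documents do not support saying that item 13 overstates or understates the benefit. The endpoint is secondary, and the primary analysis is unaffected.

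**What to change.** In section 7.1.2, item 13:

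1. Delete the chi-squared test.
2. Report the two estimated proportions descriptively, each with a confidence interval based on the number of research endoscopies behind it rather than on full group size.
3. State that tested patients and the usual-care arm are not randomised against each other, and that both proportions come from research-endoscopy attenders.
4. Replace the general-population label with *usual-care arm* in sections 2.2, 2.3 and 7.1.2.

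Optionally, add (T1 + T2 − T3)/N12 as a sensitivity analysis only. Show it over a range of Cytosponge sensitivities (the SAP itself uses 80% in item 12 and 85% in section 2.5.2) and state the instability of T3 (about 9.5 expected cases, SD about 8.4).

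The cost is a change of wording and no new data. Item 13 loses its p-value, and the intervals may be wide because section 3.4 describes the research-endoscopy sample as small.

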2.4 Level of significance

The level of significance that will be used in all the statistical analyses is 5%, two-sided. However, 95% confidence intervals will be preferred to p -values in the final report.

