As of 13th June 2019, **7844** participants were recruited in the **CLR group** (equivalent size: 2120) and **5390** in the **PLR group** after the initial 14-day opt-out period, for a total of 13,234 participants. Note that the CLR practices eventually recruited fewer patients than expected at the time of the Milestone 1 review, and that implied a higher recruitment in the PLR group, whose participants contribute more to the power of the study.

The table below shows a range of possible values for our sample size depending on how we adjust the estimate of our parameters.

	BE prevalence	Cytosponge™ TFF3 sensitivity	Endoscopy in usual care arm (over 12 months)	BE prevalence in patients getting routine endoscopy	Uptake of Cytosponge™	Intra-class correlation coefficient	Sample size if only individual randomisation	Equivalent sample size accounted for by cluster randomisation (11,816 patients in 100 practices)	Remaining sample size for PLR group
Our assumptions	4.0%	85%	10%	6%	27%	0.025	6764	2924	3840
Varying assumptions	3.9%	85%	10%	6%	27%	0.025	7098	2924	4174
	4.1%	85%	10%	6%	27%	0.025	6456	2924	3532
	4.0%	84%	10%	6%	27%	0.025	6894	2924	3970
	4.0%	86%	10%	6%	27%	0.025	6638	2924	3714
	4.0%	85%	9%	6%	27%	0.025	5658	2924	2734
	4.0%	85%	11%	6%	27%	0.025	8176	2924	5252
	4.0%	85%	10%	5%	27%	0.025	5048	2924	2124
	4.0%	85%	10%	7%	27%	0.025	9344	2924	6420
	4.0%	85%	10%	6%	26%	0.025	7190	2924	4266
	4.0%	85%	10%	6%	28%	0.025	6380	2924	3456
	4.0%	85%	10%	6%	27%	0.024	6764	3012	3752
	4.0%	85%	10%	6%	27%	0.026	6764	2840	3924

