3.4 Treatment assignment and treatment groups

Participants in the study were selected by an automated search in GP databases followed by a manual review of their records. All study subjects received an introductory letter to the study, allowing them 14 days to opt out of anonymised data collection. Following this, GP practices (for the CLR group) or participants (for the PLR group) were randomised to either receiving an invitation to the Cytosponge™ test or to usual care.

Non-responders of invitation to the Cytosponge™ were managed as were the patients in the usual care arm.

Participants with a positive Cytosponge™ result were invited to a **confirmatory endoscopy**. Negative Cytosponge™ patients were subsequently managed as were patients in the usual care arm.

Note: A small sample of patients in the usual care arm and negative Cytosponge™ patients were invited to a **research endoscopy** after the end of their follow-up period. The result of their research endoscopy is *not* part of the primary endpoint analysis. A handful of patients invited to the test were also invited to have a research

BEST3 SOP 008 – BEST3 Statistical Analysis Plan v1.0. [If this SAP has been printed or saved electronically, please check Sharepoint to ensure this version is the most up-to-date.](#)

endoscopy at the beginning of the roll-out of the procedure, but invitations to that group were stopped shortly thereafter, and any research endoscopy results in this group of patients will not be taken into account for any analyses.

4. Patient disposition

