7.1.2 Analysis of secondary endpoints

For the sake of simplicity, the cluster design of part of the Trial will be ignored for the analysis of secondary endpoints.

Any endpoints using data on BE diagnoses will rely on *actual* data available from the Trial, i.e. the methods used for data collection for the primary endpoint will not apply.

The analysis of the secondary endpoints will be further detailed in a separate supplementary SAP.

Using data from the intervention arm *only*:

- 1) Diagnostic accuracy of the Cytosponge™ according to endoscopic findings:
PPVs will be presented with 95% Clopper-Pearson (exact) confidence intervals overall, by age group/sex, by duration of acid-suppressant medication prescriptions prior to baseline and by number of columnal cells present on the sponge.
In Stata, these can be calculated using the command `diagt` or `diagti`. In R, the function `epi.tests` should be used.
- 2) Diagnostic accuracy of the Cytosponge™ test according to endoscopic and pathology findings, i.e. by score of BE severity:
PPV will be presented with a 95% exact confidence interval.
- 3) Performance of Cytosponge™ in detecting IM of the gastric cardia:
PPV will be presented with a 95% exact confidence interval.
- 4) Performance of Cytosponge™ in detecting BE or IM of the gastric cardia:
PPV will be presented with a 95% exact confidence interval.
- 5) Performance of Cytosponge™ in detecting EAC and gastric cancer:
PPV will be presented with a 95% exact confidence interval;
Numbers needed to examine (by Cytosponge™) to detect one OAC or one HGDB will also be calculated.
- 6) Sampling adequacy:
Inadequacy rate will be presented with a 95% exact confidence interval.
- 7) Endoscopy referral rates for adequate test results and successful Cytosponge™ swallows:
The two proportions will be presented with a 95% exact confidence interval.
- 8) Patient acceptability of Cytosponge™:
Proportions will be presented with a 95% exact confidence interval.
Median number of attempts to swallow per patient will be presented with interquartile range (IQR) and range.
At baseline:
 - Measures will be presented with median, IQR and range*At day 7-14:*
 - Measures will be presented with median, IQR and range
 - Differences in STAI-6 scores at day 7-14 and baseline will be compared with a Wilcoxon signed-rank test.
- 9) Physician/nurse acceptability of Cytosponge™: qualitative outcome.
- 10) Safety of Cytosponge™:

See Section 8.

11) Performance of repeat Cytosponge™ test:

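### Endpoint 13 runs a chi-squared test on counts projected from research endoscopies to whole groups, so the test cannot hold its 5% level

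*SAP*

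**What the plan says.** SAP Section 7.1.2, item 13, works in three steps.

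- For patients who received the Cytosponge, the number of undiagnosed BEs is obtained "by multiplying the proportion of BEs detected following a research endoscopy in the negative test group by the number of negative test patients".
- For usual care, it is obtained "by multiplying the proportion of BEs following a research endoscopy in the usual care arm by the number of patients in the usual care arm".
- Each number becomes a proportion, taken "out of the total number of patients in each of the two groups and will be compared using a chi-squared test".

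Section 2.4 sets the level for this test: "The level of significance that will be used in all the statistical analyses is 5%, two-sided".

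Section 3.4 describes who was invited to a research endoscopy: "A small sample of patients in the usual care arm", together with Cytosponge-negative patients. The SAP does not say how many were invited or attended.

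Two neighbouring items treat the same endoscopies differently. Item 12 sets aside direct scaling from the Cytosponge-negative endoscopies because their number is small and the result would be unstable. For the control arm it says that it will not simply scale up either. Item 15 estimates the false omission rate with the patients who attended a research endoscopy as denominator, and gives a confidence interval.

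**The concern.** A chi-squared test takes its variance from the counts and totals it is given. Here the counts are projections and the totals are whole groups, so the test treats everyone in both groups as if they had been endoscoped. The number actually endoscoped, which determines how precise the two proportions are, does not enter the calculation.

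Item 13 is a named comparison between groups. As written, the trial could report that the Cytosponge leaves significantly less, or significantly more, BE undiagnosed than usual care when the observed endoscopies show no more than chance variation.

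**Working it through.** **Inputs from the SAP**
- Recruited: "for a total of 13,234 participants" (Section 2.5.2). With 1:1 allocation (Section 2), the usual-care arm is N_U = 13,234/2 = 6,617.
- Uptake 24.0% (Section 2.5.3), so Cytosponge recipients are N_C = 0.24 × 6,617 ≈ 1,588.
- Two-sided 5% (Section 2.4).
- BE prevalence 4% (Section 2.5.2), used as the upper end for undiagnosed BE.

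**Assumptions**
- Research endoscopies per group: 25 to 800, because the SAP gives no figure.
- Common true proportion of undiagnosed BE: 1% to 4%.
- All Cytosponge recipients test-negative in the main run, and 5–10% test-positive in a variation.

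**Calibration.** Item 13 has no power or error figure of its own to reproduce. As a check on the calculations, the plan's main sample size was recomputed. The intervention proportion is 0.27 × (0.034 + 0.0009) + 0.73 × 0.006 = 1.3803%. Against 0.6%, with 90% power, this gives 6,764, as the SAP states.

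**Where the number endoscoped drops out.** Let a BEs be found in n1 endoscopies of test-negative patients (q1 = a/n1) and b in n0 endoscopies in usual care (q0 = b/n0). The plan compares p1 = q1 × N_neg/N_C with p0 = q0. Its statistic is

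(p1 − p0)² / [p̄(1 − p̄)(1/N_C + 1/N_U)].

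Neither n1 nor n0 appears in the denominator. With N_neg close to N_C, the true null variance of p1 − p0 is p(1 − p)(1/n1 + 1/n0). The standard error is therefore too small by the factor

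k = √[(1/n1 + 1/n0) / (1/N_C + 1/N_U)],

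and the large-sample false-positive rate is 2[1 − Φ(1.96/k)].

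Here 1/1,588 + 1/6,617 = 0.000630 + 0.000151 = 0.000781. With 400 endoscopies per group, k² = (2/400)/0.000781 = 6.40, k = 2.53, 1.96/2.53 = 0.775, and the rate is 44%. In this formula k reaches 1, and the test its nominal level, only if everyone in both groups is endoscoped.

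**Exact check.** The two binomials were enumerated, scaled to 1,588 and 6,617, and put through the chi-squared test without continuity correction. The last column applies the same test to the endoscoped patients themselves.

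| Endoscopies per group | k | Large-sample rate | Exact rate, null 1–4% | Exact rate, endoscoped patients only |
|---|---|---|---|---|
| 100 | 5.06 | 70% | 69–77% | 1.4–4.5% |
| 200 | 3.58 | 58% | 58–61% | 4.0–5.0% |
| 400 | 2.53 | 44% | 43–45% | 4.4–5.0% |
| 500 | 2.26 | 39% | 39–40% | 4.2–5.0% |
| 800 | 1.79 | 27% | 27–28% | 4.7–5.1% |

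With smaller samples the exact rates are 36–69% at 25 per group, 53–79% at 50 and 63–80% at 75. Unequal samples, from 50/100 to 100/300, give 62–83%. Treating 5–10% of recipients as test-positive moves the equal-sample rates by at most about 7 points. Every scenario enumerated gave more than 25%.

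**The case against.** The strongest reply concerns weight, since the text leaves no other reading of the test. This is one secondary comparison with no decision rule attached. Section 2.4 prefers confidence intervals to p-values. Section 7.1.2 promises a supplementary SAP for the secondary endpoints. Item 15 already reports the research-endoscopy result in test-negatives on the correct denominator.

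The limited reach stands: the primary analysis is untouched. The rest does not remove the problem. An interval built from the projected counts would be too narrow by the same factor k. The supplementary SAP is described as adding detail and is not available, while the chi-squared test is already fixed here. Item 15 covers one group and not the comparison.

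A reader might infer more than the documents support, in three ways.

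- **A single false-positive rate.** None can be derived, because the SAP does not give the number of research endoscopies. A range of roughly 40–75% describes about 100 to 500 per group and must carry that condition.
- **A claim about clustering.** Section 7.1.2 says that "the cluster design of part of the Trial will be ignored for the analysis of secondary endpoints", and one could apply the cluster-randomised group's ratio 7,844/2,120 = 3.7 to these outcomes. That ratio rests on an intra-class correlation of 0.025 assumed for BE, and it concerns the cluster-randomised practices only. The SAP gives no such value for the other secondary outcomes. Clustering is a separate question and enters none of the figures here.
- **That the endoscopies carry almost no information.** With several hundred per group they would carry a limited but useful amount. The fault is that the test overstates it.

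**Conclusion.** The point holds. Item 13 fixes a test whose variance comes from about 1,590 and 6,620 patients and not from those endoscoped, so it does not keep the stated two-sided 5% level. This follows from the wording alone.

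The size is conditional on the assumed number of endoscopies, on group sizes derived from 13,234 recruited, equal arms and 24% uptake, and on equal true proportions of 1–4%. Across 100 to 800 endoscopies per group the false-positive rate runs from about 77% down to about 27%. The effect is confined to this secondary endpoint.

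**What to change.** Keep the plan's point estimates: q1 × (N_neg/N_tested) for Cytosponge recipients, where N_tested is all who received the test, and q0 for usual care. Change the variance, so that each estimate draws it from the patients who had a research endoscopy:

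(N_neg/N_tested)² × q1(1 − q1)/n1 + q0(1 − q0)/n0.

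- Report the difference with a 95% interval, by bootstrap or a score or exact-type method.
- Base any test on that variance, and delete the chi-squared test on projected counts.
- Give projected numbers of undiagnosed BE only with the corresponding intervals, and state n1 and n0 beside them.

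The factor N_neg/N_tested has to stay. Comparing q1 with q0 directly would set test-negatives against all of usual care, which is a different quantity from the one item 13 defines.

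The cost is a change of SAP wording and wider intervals. No new data are needed.
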